3.2 Exclusion Criteria

- Etiology for hydrocephalus other than idiopathic normal pressure hydrocephalus
- MMSE<14
- Patients who have Tinetti gait and balance scores of <18
- Kiefer Comorbidity index>5
- Patients not capable of providing an informed consent.
- History of intra-cerebral hemorrhage

6. Drugs/ Substances/ Devices

- a. The rationale for choosing the drug and dose or for choosing the device to be used.
 CSF diversion using shunt surgery is the standard of care treatment for the normal pressure hydrocephalus
- Justification and safety information if FDA approved drugs will be administered for non-FDA approved indications or if doses or routes of administration or participant populations are changed.

n/a

- c. Justification and safety information if non-FDA approved drugs without an IND will be administered.
- d. n/a

7. Study Statistics

a. Primary outcome variable.

The primary short term outcome variable will be the Tinetti gait and balance score, the MCV Gait Grade and the gait velocity defined as number of steps per second per 30 feet walk at 6 and 12 weeks after surgery.

The primary long term outcome variable will be the Tinetti gait and balance score, the MCV Gait Grade and the gait velocity defined as number of steps per second per 30 feet walk at 6 and 12 months after surgery.

b. Secondary outcome measures.

Secondary outcome measures include the - cognitive and incontinence measures, the Black Outcome Scale, the Marmarou Recovery Scale, the functional measures of the Barthel index,

Principal Investigator: [name]

Application Number: NA_00042178

SMAF Scale and Rankin Scale, Post-Surgery Questionnaire, Kudo iNPH grading scale, Kiefer Index and European NPH Scale.

Also, outcome measures at earlier time points (i.e., the first visit 2 weeks from surgery - and 6-week follow-up) will be examined as well as the slope of the change in the measures over the follow-up.

c. Statistical plan including sample size justification and interim data analysis.

General analytic method:

For each treatment order group, we will calculate the within patient paired differences of the 6 and 12 week follow-up measures. We will examine the distributions of these summary measures, and if not normally distributed, log transformation will be tried. If near normality cannot be achieved then non-parametric analyses will be used.

Though we do not expect any carryover effects, we will first test for period effects and treatment-period interactions by testing whether the magnitudes of the mean period differences are unequal and whether the overall means for each treatment order group are different. General linear models will be used to assess treatment effect while accounting for within patient correlation. F-tests (or non-parametric Wilcoxon rank sum tests if normality cannot be achieved) will be used to test significance of treatment effects.

Specifically for the primary outcome:

We will calculate the within patient difference in the Tinetti gait score, the MCV Gait Grade and the gait velocity at 6 weeks (end of first treatment period) and at 12 weeks (end of second treatment period). This difference is the same as it would be if we calculated the change from baseline at each time period. General linear model analysis will be employed to test for period and treatment effects and the interaction, while accounting for within patient correlation. If there is no period effect, then the analysis can be simplified to reporting a paired t-test of the difference in the Tinetti gait score, the MCV Gait Grade and the gait velocity between the optimal and sub-suboptimal 6-week follow-up. If any patient is a treatment failure and is discontinued from a treatment arm, the measure at the time of failure will be carried forward to the 6-week measure.

Sample size calculation:

A mean difference in the Tinetti score of 5 points would be considered clinically meaningful. Given the inclusion criteria of a baseline Tinetti score of >18 and data from our clinic, we estimate the standard deviation for the change to be 5 points. Using a two-sided t-test with the Type I error level of 0.05, we will have 80% power to reject the null hypothesis of no difference when the total sample size of a 2x2 crossover design is 34. Adjusting for a dropout rate of 20% a sample size of 42 study subjects would be required.

Principal Investigator: [name]

Application Number: NA 00042178

1. Boon, A., et al. Dutch normal-pressure hydrocephalus study: prediction of outcome after shunting by resistance to outflow of cerebrospinal fluid. *J Neurosurg* **87**, 687-693 (1997).

- 2. McGirt, M., et al. Diagnosis, treatment, and analysis of long-term outcomes in idiopathic normal-pressure hydrocephalus. *Neurosurgery* **62 Suppl 2**, 670-677 (2008).

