NCT01798641

PI: [name]

Date: March 19, 2013

Principal Investigator: [name]

Application Number: NA 00042178

Protocol March 19th, 2013

Johns Hopkins Medicine - eForm A

 Use the section headings to write the eForm A, inserting the appropriate material in each. If a section is not applicable, leave heading in and insert N/A.

 When submitting eForm A (new or revised), enter the date submitted to the field at the top of eForm A.

1. Abstract

Normal Pressure Hydrocephalus (NPH) is a treatable cause of dementia, gait apraxia and urinary incontinence that results in significant disability if not identified and treated. The pathogenesis of this disease is poorly understood it may involve ischemia damage caused by impaired cerebral blood flow following compression damage to the periventricular white matter. The shunting of CSF using ventriculoatrial (VA) or ventriculoperitoneal (VP) shunt is a commonly employed treatment of NPH. However, accurate diagnosis and selection of patients with shunt responsive NPH is critical for a favorable outcome following shunt surgery. The standard diagnostic tests for NPH such as clinical and radiological findings have proven to be less accurate than desired, with many patients remaining undiagnosed or untreated while others receive treatment due to a falsepositive diagnosis. The response rates to shunting have been reported to vary between 31% to 89%. Furthermore, long term follow-up studies have shown loss of response to shunt which may be due to the natural history of disease, progression of comorbidities or a short term placebo effect following shunt surgery. The aims of this study are to determine (a) patient improvement in gait and other clinical measures in response to active shunt compared to placebo (non-active shunt) (b) predictors of response to shunt (c) long-term outcomes of patients with shunt (d) pilot assessment of sensitivity and specificity of commonly used scales to evaluate NPH. We propose a randomized double-blind cross-over study with a suboptimally draining/non-functioning shunt arm (equivalent of placebo) and an optimally draining/functioning shunt arm. Patients will be followed for 6 weeks on the first arm and then crossed over to the second arm and followed for an additional 6 weeks for the primary aim. Patients will then be followed for two years. Clinical outcomes include changes in gait, cognition, incontinence and functional independence.

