Objectives (include all primary and secondary objectives)
 Primary Outcome:
 Changes in Gait

Outcome Measure:

Gait

Tinetti Tool Timed Up and Go task (TUG) MCV Gait Grade

Principal Investigator: [name]

Application Number: NA_00042178

Cognition

Mini Mental State Examination (MMSE)
Rey Auditory Verbal Learning Test (RAVLT)
Trail Making Test A & B
Writing the Alphabet
Beck Depression Inventory
Stroop test
Pegboard

Urinary

Urinary Incontinence Questionnaire (ICIq-UI)
Overactive Bladder Questionnaire (ICIq-OAB)
Quality-of-Life related to lower urinary tract symptoms (ICIq-LUTSqoI)
Global quality-of-life assessment (AUASSqoI)
Voiding diary

Functional Scales

Barthel Index Modified Rankin Scale SMAF Scale of Functional Autonomy

iNPH Scales

Kudo INPH grading Scale Kiefer Index (Gait/balance, headache and dizziness domains)

Outcome Scales

Black Outcome Scale Marmarou Recovery Scale Post-Shunt Surgery Questionnaire

European NPH scale

Core imaging testing:

Sagittal MPRAGE
Axial T2
Axial FLAIR
Sagittal CISS midline

Sagittal phase contrast through the midline

Principal Investigator: [name]

Application Number: NA_00042178

Axial through plane cardiac gated phase contrast imaging aqueduct DTI 30 directions 1 nex

Comorbidity Index

iNPH Diagnosis Checklist

3. Background

Normal Pressure Hydrocephalus (NPH) is a treatable cause of dementia, gait apraxia and urinary incontinence that results in significant disability if not identified and treated. The pathogenesis of this disease is poorly understood but may involve ischemia caused by impaired cerebral blood flow following strain in fibers of periventricular white matter. The standard diagnostic tests for NPH such as clinical and radiological findings have proven to be less accurate than desired, and many patients may remain undiagnosed and untreated. The symptoms of NPH are necessary but not sufficient to diagnose NPH and recommend shunt surgery. CT and MRI findings are not specific for NPH because they overlap with findings of cerebral atrophy or vascular dementia.

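### Three gait variables share the short-term primary outcome with no rule for declaring success, and the stated power covers the Tinetti score only

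*Combined protocol and SAP*

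**What the plan says.** Section 7a (Primary outcome variable) reads: "The primary short term outcome variable will be the Tinetti gait and balance score, the MCV Gait Grade and the gait velocity", assessed at 6 and 12 weeks. The next sentence of 7a names the same three variables as the primary long-term outcome at 6 and 12 months.

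Section 7c (Specifically for the primary outcome) gives all three the same analysis: a general linear model, which reduces, if there is no period effect, to "a paired t-test of the difference in the Tinetti gait score, the MCV Gait Grade and the gait velocity" between the two drainage states. Under the general analytic method, F-tests or Wilcoxon rank sum tests "will be used to test significance of treatment effects". No order, composite or adjustment is mentioned.

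The sample size paragraph of 7c concerns one variable only: "A mean difference in the Tinetti score of 5 points would be considered clinically meaningful", with an SD for the change of 5 points. It continues: "Using a two-sided t-test with the Type I error level of 0.05", "we will have 80% power to reject the null hypothesis of no difference" with 34 patients in total, or 42 after allowing for 20% dropout.

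The rest of the document does not settle the matter. Section 2 gives the primary outcome as "Changes in Gait". Aim (a) in the abstract is "patient improvement in gait and other clinical measures in response to active shunt compared to placebo" and names no variable.

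**The concern.** With three primary variables, the plan needs to say which pattern of results makes the trial positive. It could be any one variable, a named one, or all three, and each choice has different error and power.

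- **Any one suffices.** Three tests at 0.05 give a false-positive risk above 5%.
- **All three are required.** Error is at most 5%, but the stated power was calculated for one variable and does not carry over.
- **The three disagree.** The plan then defines no conclusion, and the decisive measure could be chosen after the results are known.

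This matters here because the protocol justifies the trial by widely varying earlier response rates and the lack of a placebo-controlled evaluation (sections 3 and 4e).

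**Working it through.** **Inputs from the documents (section 7c unless noted).** Three primary variables (7a); two-sided 0.05; Tinetti difference 5 and SD 5; total N = 34; 1:1 allocation (section 4a). The documents give no correlations among the three variables, and no effect size or SD for MCV Gait Grade or gait velocity. Values used for these below are assumptions.

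**1. The plan's own figure.** Take a two-sample t-test with 17 + 17 patients. The noncentrality is 5 / (5 × √(2/17)) = 2.915, with 32 degrees of freedom and critical value 2.037. Power is 80.7%; with 16 + 16 it is 78.1%. So N = 34 reproduces, for Tinetti alone. For dropout, 34/0.8 = 42.5, against the stated 42.

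**2. What the SD of 5 could mean.** For a 2x2 crossover with 34 completers, noncentrality is 5√34 / SD of the within-patient difference.

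| Reading of the 5 points | SD of difference | Noncentrality | Tinetti power at 0.05 |
|---|---|---|---|
| Basis that reproduces N = 34 | 10 (equivalent) | 2.915 | 80.7% |
| Within-patient SD | 5√2 = 7.07 | 4.123 | 97.9% |
| SD of the within-patient difference | 5 | 5.831 | above 99.9% |

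**3. Any one of three suffices.** With independent tests, the risk is 1 − 0.95³ = 14.3%. With common correlation ρ and normal test statistics, it is 1 − ∫ [Φ((1.96 − √ρ·x)/√(1−ρ)) − Φ((−1.96 − √ρ·x)/√(1−ρ))]³ φ(x) dx.

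| Assumed ρ | 0 | 0.5 | 0.8 | 0.9 | 0.95 | 0.99 |
|---|---|---|---|---|---|---|
| False-positive risk | 14.3% | 12.5% | 9.8% | 8.4% | 7.3% | 6.0% |

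Simulated t-tests with 17 + 17 patients agree at ρ = 0 to 0.9 (14.3% to 8.4%).

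**4. All three required.** Joint power cannot exceed the power of any one component, so it cannot exceed Tinetti's own power in step 2. Beyond that it depends on the assumed power of the other two variables:

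| Assumed power (Tinetti; other two each) | Joint power, ρ = 0 to 0.9 |
|---|---|
| 80%; 80% | 51.2% to 72.2% |
| 80%; 50% | 20.0% to 42.8% |
| 80%; 95% | 72.2% to 79.8% |
| 99.99%; 50% | 25.0% to 42.8% |
| 99.99%; 95% | 90.2% to 93.2% |

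At 80% each and ρ = 0, all three succeed with probability 0.8³ = 0.512 and none with 0.2³ = 0.008. The results are therefore split in 1 − 0.512 − 0.008 = 48.0% of trials. At ρ = 0.9 the split falls to 15.0%.

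**5. Fixed order starting with Tinetti.** A false-positive claim on the first variable has probability 0.05, and nothing later is tested unless the first is significant. Overall error under the joint null is 5% at any correlation; simulation gave 4.9% to 5.0%.

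**The case against.** The best defence is that Tinetti already leads. It alone has a meaningful difference, an SD, a significance level and power, and it also defines eligibility and treatment failure. That makes the likely intention easier to guess. But a powering choice is not a decision rule: sections 7a and 7c treat the three variables alike, and nothing says that the other two cannot establish success.

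A second objection is that the 8% to 14% is hypothetical, and this stands. A reader might infer that the plan adopts an any-one rule and so runs at that error rate. The documents do not support this: they neither state nor exclude such a rule, and they give no correlations. The figure also assumes one clean test per variable, whereas 7c plans period and interaction pre-tests, a log transformation and a non-parametric fallback.

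A third objection also stands. It is tempting to say that requiring all three caps power at 80%, or that splitting the significance level must cost Tinetti much power. Both hold only on the reading of the SD that reproduces N = 34. If 5 points is the SD of the within-patient difference, Tinetti power is far higher and a split costs it almost nothing.

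**Conclusion.** The omission is real and should be corrected before analysis. The plan has three unranked short-term primary variables, no definition of a positive trial, and power for one of them. This follows from the text and needs no assumption.

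The size does need assumptions. Under an any-one rule the risk is 14.3% at correlation 0 and 8.4% at 0.9, and it still exceeds 5% at 0.99 (6.0%). Under an all-three rule the error is at most 5%. Joint power is then limited by Tinetti's own power (about 80%, or higher, depending on the SD reading) and cannot be computed without effect sizes and SDs for the other two variables. These figures show what the missing rule could mean; they do not estimate this trial's error rate or power.

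**What to change.** **Change to 7a and 7c.** Name the Tinetti difference between optimal and sub-optimal drainage, measured at the end of each 6-week period, as the single primary outcome at two-sided 0.05, as the sample size already assumes. Test MCV Gait Grade and gait velocity afterwards in a prespecified fixed order of the sponsor's choice, each at 0.05 and only if the one before is significant. In the same edit, relabel the 6- and 12-month primary variables in 7a as secondary, so that no second unranked primary set remains.

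**Cost.** Wording only; N and Tinetti power do not change. The downside is that a result significant only on MCV Gait Grade or gait velocity could not be claimed as a primary success.

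**Alternatives.** An explicit all-three rule needs effect sizes and SDs for the other two variables and a new power statement. An equal split (0.05/3 = 0.0167 each) has a cost that depends on the SD reading. With 34 completers, Tinetti power goes:

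- from 80.7% to 65.2% on the basis that reproduces N = 34, where restoring 80% needs 46 completers (81.2%);
- from 97.9% to 93.8% if 5 is the within-patient SD;
- from above 99.9% to 99.9% if 5 is the SD of the within-patient difference.

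Holm's step-down version rejects whenever the equal split does, so it loses no more than this.

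**Separate item.** Gait velocity is absent from the gait measures listed in sections 2 and 4f, which list TUG instead. These sections and 7a should be reconciled; the multiplicity fix does not resolve this.

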treatment failure as this is considered under standard of care to be high risk of fall.
Additionally any patient falling due to inability to balance or poor gait would also be
considered a treatment failure.

Any patient deteriorating to failure level or having a fall attributable to gait impairment will be recorded as a treatment failure for that arm of the study and if on suboptimal drainage arm will be crossed over to optimal drainage level.

Patients who fail would however continue to participate in study and data will be collected at all subsequent follow-up points regardless of the study arm as described above. Furthermore, for concerns of patient safety no patient who fails (Tinetti \leq 18) will subsequently have suboptimal drainage in shunt at anytime^{12,13}.

Response:

Gait

- Tinetti gait and balance scale: Measured with respect to baseline (pre-drainage trial scores)
- 2. TUG: Measured with respect to baseline (pre-drainage trial scores)
- 3. MCV Gait Grade: Measured with respect to baseline (pre-drainage trial scores)

Cognition

- 1. Mini Mental State Examination (MMSE)
- 2. Rey Auditory Verbal Learning Test (RAVLT): Measured with respect to baseline (pre-drainage trial scores)
- 3. Trail Making Test A & B: Measured with respect to baseline (pre-drainage trial scores)
- 4. Writing the Alphabet: Measured with respect to baseline (pre-drainage trial scores)
- 5. Beck Depression Inventory

Principal Investigator: [name]

Application Number: NA 00042178

- 6. Stroop test
- 7. Pegboard

Urinary

- 1. Urinary Incontinence Questionnaire (ICIq-UI): Measured with respect to baseline (predrainage trial scores)
- 2. Overactive Bladder Questionnaire (ICIq-OAB): Measured with respect to baseline (predrainage trial scores)
- 3. Quality-of-Life related to lower urinary tract symptoms (**ICIq-LUTSqol**): Measured with respect to baseline (pre-drainage trial scores)
- 4. Global quality-of-life assessment (**AUASSqol**): Measured with respect to baseline (predrainage trial scores)
- 5. Voiding Diary

Functional Scales

- 1. Barthel Index: measured with respect to baseline (pre-drainage trial scores)
- 2. Modified Rankin Scale
- g. Description of what happens to participants receiving therapy when study ends or if a participant's participation in the study ends prematurely.
- Inclusion/Exclusion Criteria3.1 Inclusion Criteria

 - Age of Patients (between 55 to 85 years old)
 - Clinically suspected iNPH with at least gait impairment.

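### The primary outcome called gait velocity is defined as steps per second, which is cadence, so a patient who walks faster with longer steps can score as unchanged or worse

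*Combined protocol and SAP*

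**What the plan says.** Section 7a of the protocol names three primary variables: "The primary short term outcome variable will be the Tinetti gait and balance score, the MCV Gait Grade and the gait velocity". The third is specified for the short term as "the gait velocity defined as number of steps per second per 30 feet walk at 6 and 12 weeks after surgery" and for the long term as "the gait velocity defined as number of steps per second per 30 feet walk at 6 and 12 months after surgery". Section 7c takes it into the primary analysis without redefining it: "We will calculate the within patient difference in the Tinetti gait score, the MCV Gait Grade and the gait velocity at 6 weeks", and again at 12 weeks. Nowhere do the documents define it as distance over time, add step length, or state whether a higher or a lower value is an improvement.

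The 30-foot walk appears only in section 7a. The gait list under Objectives (section 2) reads "Tinetti Tool Timed Up and Go task (TUG) MCV Gait Grade", and the gait response list in section 4f names the same three instruments, including "TUG: Measured with respect to baseline (pre-drainage trial scores" and so on. TUG is not among the primary variables in section 7a or the secondary measures named in section 7b.

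**The concern.** Velocity is distance divided by time. The definition counts steps instead of feet, so step length drops out. A shunt effect on walking speed that comes through longer steps would be understated, missed or reversed. Quicker, shorter steps would raise the measure without any gain in speed.

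The F-tests and the paired t-test in section 7c would run regardless, because they need no stated direction. The difficulty is in reading the result: a significant difference in this variable could not be classed as benefit or harm from the plan, and it could not be reported as a difference in gait velocity. Choosing the meaning after seeing the data would leave room for selecting the outcome.

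**Working it through.** **The plan's own figure.** The documents give no effect size, SD or power for gait velocity. The sample size uses the Tinetti score only: "A mean difference in the Tinetti score of 5 points would be considered clinically meaningful", and "we estimate the standard deviation for the change to be 5 points". With difference 5, SD 5, two-sided alpha 0.05 and 80% power, a two-group t-test needs 16.7, so 17 per group, 34 in total (power 0.807). This matches the stated 34. Dropout of 20% gives 34 / 0.8 = 42.5, against the stated 42. Gait velocity does not enter, so correcting its definition leaves the sample size alone.

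**Formulas.** Let D = 30 ft (section 7a), N the number of steps and T the time in seconds.

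- Speed: v = D / T
- Step length: L = D / N
- Measure as defined: c = N / T = (D / L) / (D / v) = v / L
- Relative change in c: (1 + change in v) / (1 + change in L) − 1

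If the phrase about 30 feet is read as a further division by 30, c is only rescaled by a constant (2.0 steps/s becomes 2.0 / 30 = 0.067) and every percentage change stays the same. Neither reading gives feet per second.

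**Worked cases.** The step counts and times are assumptions; the documents give none.

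| Case | Before | After | Step length (ft) | Speed (ft/s) | Measure as defined (steps/s) |
|---|---|---|---|---|---|
| 1. Faster, longer steps | 30 steps, 15 s | 20 steps, 10 s | 1.00 to 1.50 | 2.0 to 3.0 (+50%) | 2.0 to 2.0 (0%) |
| 2. Faster, much longer steps | 30 steps, 12 s | 22 steps, 10 s | 1.00 to 1.36 | 2.5 to 3.0 (+20%) | 2.5 to 2.2 (−12%) |
| 3. Faster, same steps | 30 steps, 20 s | 30 steps, 15 s | 1.00 to 1.00 | 1.5 to 2.0 (+33%) | 1.5 to 2.0 (+33%) |
| 4. Slower, shorter steps | 30 steps, 20 s | 50 steps, 25 s | 1.00 to 0.60 | 1.5 to 1.2 (−20%) | 1.5 to 2.0 (+33%) |

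**Range for a true speed gain of 20%.**

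| Change in step length | Change in the measure: 1.20 / (1 + change) − 1 |
|---|---|
| 0% | +20% |
| +10% | +9.1% |
| +20% | 0% |
| +30% | −7.7% |
| +50% | −20% |

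The measure follows speed exactly only if step length does not change. It understates the gain when step length rises by less than speed, is flat when the two rise in proportion, and reverses when step length rises by more.

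**The case against.** The strongest reply is about size. Cases 1 and 2 use chosen values and need step length to rise by 50% and about 36%. With little change in step length the measure moves the right way, merely attenuated. That stands: the algebra shows what can happen, not how often, and the documents do not allow the frequency to be estimated.

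Second, the damage is contained. The Tinetti score and the MCV Gait Grade are also primary and do not depend on this definition; the sample size and the treatment-failure rule do not use gait velocity. That also stands, but one of the three named primary variables remains mis-specified.

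Third, the wording may be loose drafting for a timed 30-foot walk with steps counted. That is possible, and speed could then be recovered from the recorded time. But the definition is given twice and not corrected in section 7c, so an analyst who follows it would compute cadence.

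Fourth, the mismatch between the gait lists is a separate matter, and the visit flow chart in section 4a was not readable in the text available here, so it cannot be said that the walk is unscheduled. This is accepted. The mismatch is a secondary consistency point, and the conclusion does not rest on it.

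**Conclusion.** The concern holds. As written, the variable is speed divided by step length. In the assumed cases, a 50% gain in speed scores as no change, a 20% gain as a 12% decline, and a 20% loss as a 33% rise. The algebra needs no assumption beyond the fixed 30-foot distance; the particular percentages depend on the assumed step counts and times. Because this is a named primary outcome at 6 and 12 weeks and again at 6 and 12 months, the definition must be corrected before analysis. The effect is confined to this one variable.

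**What to change.** In section 7a, in both the short-term and the long-term statement, define gait velocity as 30 feet divided by the time in seconds taken to walk 30 feet, in ft/s, and state that a higher value is better. If step rate is of interest, list it separately as cadence, as a descriptive measure. Settle this before anyone sees outcome data by treatment.

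Add the timed 30-foot walk to the gait lists in sections 2 and 4f, and state the role of TUG, which those lists contain and section 7a omits.

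Cost: wording in three sections and no change in sample size. At 6 and 12 weeks and 6 and 12 months the present definition already requires a step count and a time, so nothing new is measured. The baseline visit should be checked. The 6-versus-12-week contrast needs no baseline walk, as section 7c itself notes that the within-patient difference is the same with or without subtracting baseline. The 6- and 12-month outcomes have no randomised comparator and need a baseline value to show change. If the walk is not already done at baseline, one timed walk has to be added there.

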During the initial phase of the study, participants will be randomized in 1:1 allocation ratio to optimally and sub-optimally draining shunt arms. After completion of six weeks the opening pressures for patients in the optimally draining shunt arm will be raised to minimize CSF flow (crossover to sub-optimally draining arm). Likewise, at 6 weeks patients initially in suboptimal drainage arm will have the opening pressures appropriately reduced so that flow through the shunt is optimal (crossover to optimal drainage shunt arm). X-rays will be performed to confirm shunt valve settings. Since the shunt is only effective during the time it is effectively draining and the carryover effect is minimal (i.e., often lasting for no more than a few days), there will be no washout period between arms. Patients will undergo every third week evaluations regardless of the study arm to evaluate safety as well as efficacy. Patients and the psychometrician, physical therapist and nurse practitioner who assess the outcome measures will be blinded to the shunt status. Only the study neurosurgeon and neurologist will be aware of the shunt status, and will make clinical (safety) decisions after being informed of Tinetti gait and balance scores. The follow-up and evaluation timeline is indicated in the algorithm above. The Neurosurgeon will be notified about the gait and balances score and will make a clinical (safety) decision accordingly. Any patient whose gait deteriorates to Tinetti < 18 or has a fall will be regarded as a treatment failure. Patients who are a treatment failure during the

Principal Investigator: [name]

Application Number: NA 00042178

suboptimal drainage arm will have the opening pressure of the valve adjusted. These patients would then be considered to be crossed over to draining arm if they were in the initial suboptimal drainage arm of the study. If a patient who has already been crossed over from optimally draining shunt to sub-optimally draining shunt arm worsens, s/he will have the shunt pressure turned down and will be followed according to standard of care protocol at 6 monthly intervals. During this time, we will collect data on these follow-up visits as part of the research.

Standard of care procedures: Shunt surgery, Post op evaluations while shunt is in optimal drainage setting, 6, 12 months, 18 months and 24 months post-op visit

Research procedures: Visits during non-draining shunt period

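### The early-switch rule is written for the primary gait outcomes only; read literally, the general method puts on-drainage values in the non-draining position for secondary outcomes

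*Combined protocol and SAP*

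**What the plan says.** Section 7c (General analytic method) sets the analysis for all outcomes: "For each treatment order group, we will calculate the within patient paired differences of the 6 and 12 week follow-up measures". It gives no rule there for patients whose valve is reset before the planned crossover.

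The one such rule comes later in 7c, at the end of the paragraph headed "Specifically for the primary outcome", which deals with Tinetti, MCV Gait Grade and gait velocity. For a patient who fails and leaves a treatment arm, "the measure at the time of failure will be carried forward to the 6-week measure".

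Section 7b lists the secondary outcomes, among them "cognitive and incontinence measures, the Black Outcome Scale, the Marmarou Recovery Scale, the functional measures of the Barthel index". It also plans to examine earlier visits and "the slope of the change in the measures over the follow-up".

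Section 4a has the valve adjusted for patients who fail on suboptimal drainage: "These patients would then be considered to be crossed over to draining arm if they were in the initial suboptimal drainage arm". When the failure comes after the crossover to suboptimal drainage, 4a moves the patient to six-monthly follow-up. Section 4f says that after failure "data will be collected at all subsequent follow-up points regardless of the study arm", and that a patient who has failed is not put on suboptimal drainage later.

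**The concern.** A patient who starts non-draining, fails at the visit within 2 weeks of surgery and is switched has had about 4 weeks of drainage by week 6 (6 - 2 = 4). The week-6 cognitive, urinary and functional scores are then on-drainage scores, and so are those at week 12. A difference taken by treatment order group still treats week 6 as the non-draining period.

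The patients affected are those whose gait did worst without drainage. If their pairs carry no treatment contrast, the estimated effect on the secondary outcomes shrinks toward zero, while the gait outcomes have at least a partial safeguard. A gait benefit beside weak results elsewhere could then be read as a finding about what shunting does, when part of it comes from handling the same patients in two ways. The abstract names cognition, continence and functional independence as clinical outcomes beside gait.

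**Working it through.** **Plan's own figure.** The plan gives no failure rate and no figure on this point. Its total of 34 (17 per group in a two-sample t-test with difference 5 and SD 5, power 80.7%) concerns the Tinetti score and neither supports nor weakens the concern.

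**Step 1: where each value comes from.** Visits are taken from Section 4b, switching from 4a and 4f. A failure found at a scheduled end-of-period visit is taken to be measured before the valve is reset.

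| Sequence and time of failure | Week 6 | Week 12 | Pair under the general method |
|---|---|---|---|
| Non-draining first, before week 6 | on drainage | on drainage | drainage v drainage |
| Non-draining first, found at week 6 | non-draining | on drainage | as intended |
| Draining first, after week 6 and before week 12 | on drainage | on drainage (4f) or not taken (4a) | drainage v drainage, or no pair |
| Draining first, found at week 12 | on drainage | non-draining | as intended |
| Draining first, before week 6 | on drainage | on drainage, since 4f rules out later suboptimal drainage | drainage v drainage |

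The last row affects all outcomes. The carry-forward sentence does not clearly cover it even for gait, and it is left out of f below.

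**Step 2: dilution.** Assumptions:
- f is the share switched early in the non-draining period, before its end-of-period visit, and is the same in both sequences.
- Drainage has its full effect by the next visit.
- Two on-drainage values differ by zero on average.
- d is the true effect in patients who do not fail.

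Failures have the same effect d (true mean d):
- Week-12 values of period-2 failures on drainage: (1-f)d / d = 1-f.
- Those values missing, sequences weighted equally: ½[(1-f)d + d] / d = 1-f/2.

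Failures have twice the effect (true mean (1-f)d + 2fd = (1+f)d):
- On drainage: (1-f)/(1+f).
- Missing: (1-f/2)/(1+f).

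| f | 1-f | 1-f/2 | (1-f)/(1+f) | (1-f/2)/(1+f) |
|---|---|---|---|---|
| 10% | 0.90 | 0.95 | 0.90/1.10 = 0.82 | 0.95/1.10 = 0.86 |
| 20% | 0.80 | 0.90 | 0.80/1.20 = 0.67 | 0.90/1.20 = 0.75 |
| 30% | 0.70 | 0.85 | 0.70/1.30 = 0.54 | 0.85/1.30 = 0.65 |

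**Step 3: could f be more than trivial?** Entry requires Tinetti above 18. Section 4f sets failure at 18 or below, 4a at below 18. A patient entering at 19 fails after losing one point under 4f (19 - 1 = 18) or two under 4a (19 - 2 = 17), and a fall can also count as failure. The planning SD for change is 5 points. This does not estimate f, but it gives no ground for assuming f is near zero. The two thresholds must be reconciled.

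**The case against.** The strongest reply is that silence is not a plan. A reader might infer that the plan directs every secondary outcome of every switched patient to be counted as non-draining. The documents do not support that. Section 4a treats early switchers from the first period as crossed over, which points toward crediting later values to drainage. The general linear model in 7c is not said to code treatment as scheduled or as actually set. The carry-forward sentence opens with any patient and may have been meant more widely. All of this stands. What remains is that no rule is written for these outcomes, and the one procedure that is written gives the drainage-with-drainage pair.

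Other parts of the reply also stand:
- A reader might infer that failures make the slope mix the two settings. A slope across 12 weeks spans both settings for every patient by design, so failures are not the cause.
- Gait is not fully protected. The sentence refers to the 6-week measure, and how it applies to a failure in the second period is unclear.
- An as-scheduled comparison is a recognised, conservative choice. It would need to be stated as the choice, and its difference from the gait analysis explained.
- A pre-switch value may come from 2 weeks after surgery and be set against week 12, which mixes recovery time with treatment.
- The text does not show that the full battery is taken at an unscheduled failure assessment.

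**Conclusion.** The concern holds as a gap with a predictable consequence. There is no early-switch rule for secondary outcomes, and the general method, followed literally, pairs drainage with drainage for a non-draining-first patient who fails before week 6. For a draining-first patient who fails between weeks 6 and 12, the outcome is open until 4a and 4f are reconciled: an on-drainage value or a missing one.

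On the assumptions above, with f from 10 to 30%, the secondary effects keep 70 to 95% of their true size if failures respond like other patients, and 54 to 86% if they respond twice as strongly. The failure rate, the doubling and the full effect by the next visit are all assumed. The direction under the literal method is toward no effect. The point should be corrected before analysis. It does not touch the sample size figure.

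**What to change.** - Move the early-switch rule from the primary-outcome paragraph to the general method, so that it covers all outcomes and the end of either period (week 6 or week 12).
- Record the valve setting in force at each assessment.
- For secondary outcomes, take as the non-draining value the last post-operative assessment made under that setting. Include the assessment that triggers the switch if the measure was taken then, and never use a value taken after it.
- If no such value exists (a fall before the first visit, or a draining-first patient who never enters the non-draining period), treat the non-draining value as missing. Do not put an on-drainage value in its place.
- Report the as-scheduled difference between weeks 6 and 12 as a sensitivity analysis.
- Fit any slope within a valve setting.
- Reconcile 4a and 4f on assessments after a second-period failure and on the failure threshold.

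The cost is SAP wording and one data field, plus the secondary measures at failure assessments if these are not already taken there. Section 7b already plans to use the 2-week visit, so pre-switch values should often exist. The downside should be stated in the plan: some non-draining values will come from week 2 or week 9, so recovery time or practice is partly mixed with treatment and may bias in either direction.
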